## Version history

Version	Date	Section number changed	Description/Changes made
1.0	19-SEP-2024		Final version, signed
0.9	18-SEP-2024	5.4	Mediation analysis revised
0.3	12-SEP-2024	5.4; various	Prefinal version: Mediation analysis updated; Proposed changes incorporated throughout the document
0.2	10-SEP-2024		Update after Review
0.1	03-MAY-2024		First draft

## Abbreviations

ACE-D	Adverse Childhood Experiences Questionnaire
BFI-10	Big Five Inventory-10
DSM-5	Diagnostic and Statistical Manual of Mental Disorders, Fifth Edition
EFS	Evaluated for Safety Set
ERQ	Emotion Regulation Questionnaire
FAS	full analysis set
FIML	full information maximum likelihood
IBS	Irritable bowel syndrome
IBS-SSS	irritable bowel syndrome severity scoring system
IEC	Independent Ethics Committee
IRB	Institutional Review Board
ITT	Intention-to-treat
NRS	Numeric rating scale
PANAS	Positive and Negative Affectivity Schedule
PHQ-15	Patient Health Questionnaire-15
PM	percentage mediated
PP	Per Protocol
PSS10	Perceived Stress Scale
RCT	Randomised Controlled Trial
SAP	Statistical Analysis Plan
SC	Standard Care
SCCAI	Simple Clinical Colitis Activity Index
SD	Standard Deviation
SSD-12	Somatic Symptom Disorder - B Criteria Scale
TAS-20	Toronto Alexithymia Scale
TE	treatment effect
TEX-Q	Treatment Expectation Questionnaire
TNF- $\alpha$	tumor necrosis factor
UC	Ulcerative colitis
WI-7	Whiteley-Index Short version

# 1 Introduction

This Statistical Analysis Plan (SAP) is based on the published study protocol ([name], et al., 2022) and follows the guideline for statistical analysis plans (Gamble, et al., 2017).

Some points of the statistical methods and of the study design are already described in the study protocol. This Statistical Analysis Plan (SAP) aims to further specify the procedures and statistical methods applied during the final analysis of the study data.

## 1.1 Background and rationale

Ulcerative colitis (UC) and irritable bowel syndrome (IBS) are two distressing chronic diseases with considerable overlap concerning their gastrointestinal symptoms, in particular abdominal pain and altered bowel habits. There is good evidence to assume that, across both diseases, increased levels of illness-related anxiety and dysfunctional symptom expectations contribute to the persistence of gastrointestinal symptoms.

## 1.2 Objectives

Since both factors can potentially be modified by targeted interventions, this study will investigate defined mechanisms of action; namely, whether persistent gastrointestinal symptoms in UC and IBS can be influenced by modifying dysfunctional symptom expectations and illness-related anxiety. Studying a primarily inflammatory and a primarily functional bowel disease in parallel allows for the investigation of whether the same mechanisms of symptom persistence are involved for these two different, yet related diseases.

# 2 Study Methods

## 2.1 Trial design

SOMA.GUT-RCT is a three-arm randomised controlled trial (RCT) in 117 patients with UC and 117 patients with IBS, totalling 234 patients. In order to identify the effect of a targeted modification of illness-related anxiety and dysfunctional symptom expectations on persistent gastrointestinal symptoms and to differentiate this effect from general modes of action, a randomised comparison between a specifically treated group, a group treated non-specifically in the same dose and a control group without additional treatment must be conducted. A control group is necessary to test whether the experimental

interventions have a positive effect compared with no intervention, to investigate further risk factors and to allow comparisons of risk factors across diseases. Thus, we will use the design of a three-arm randomised controlled trial, in which 33% of each disease group will undergo targeted expectation management in addition to standard care (SC), 33% will undergo non-specific supportive treatment in addition to SC, while 33% will receive SC only (Figure 1). In the control group, we will additionally investigate the contribution of predefined risk factors to gastrointestinal symptom persistence. The study will be monocentric and entail nationwide recruitment. This study is part of the SOMACROSS research unit (FOR 5211), funded by the German Research Foundation (Deutsche Forschungsgemeinschaft, DFG) which investigates mechanisms of somatic symptom persistence across different medical conditions.

The study protocol was approved by the Ethics Committee of the Hamburg Medical Association on 25 January 2021 (reference number: 2020-10198-BO-ff). The trial will be conducted in accordance with the Declaration of Helsinki, guidelines for Good Clinical Practice, national and local laws. Before inclusion, eligible participants will be informed about the course of the study verbally and in written form and they will provide written informed consent. The data will be stored in pseudonymised form. Any changes to the study protocol will be listed in the study registry and publications.

[figure not shown]

Figure 1: Planned flow of participants through the course of the study. \*Outcomes after 6 and 12 months are secondary and were not included in the sample size estimation. GUT.EXPECT, expectation management intervention; GUT.SUPPORT, supportive intervention

## 2.2 Randomization

Patients were randomized in a 1:1:1 ratio using central block-wise randomization with variable block length to targeted expectation management and standard care, non-specific supportive treatment and standard care or to standard care only (control). The randomization is performed directly after baseline data collection.

## 2.3 Sample size

This trial is powered with regard to the difference between intervention 1 (GUT.EXPECT+SC) versus the control condition (SC). Based on the literature reviewed, we assume a within-group standard deviation (SD) of 75 points on the irritable bowel syndrome severity scoring system (IBS-SSS). Given this SD, a difference of 40 points on the IBS-SSS can be detected with a power of 80%, using a two-sided alpha of 5%, by including 29 patients per group, yielding a total sample size of n=87 for UC and IBS, respectively. Based on the results of our prospective cohort study, we assume a loss to follow-up between baseline and the primary outcome measurement (ie, 3 months follow-up) of 25%, resulting in a total of n=117 randomised patients for UC and IBS, respectively. Assuming that 50% of patients with UC or IBS will meet the inclusion criteria, n=234 patients per diagnostic group will be assessed for eligibility.

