## 5.2 Analysis methods

### 5.2.1 Primary outcome

An analysis of covariance will be used to investigate the group differences in the IBS-SSS, adjusted for baseline IBS-SSS. The underlying disease (UC vs IBS) and sex will be added as additional factors. Assuming no interaction effect between disease and treatment group, this is more effective than analysing both disease conditions independently. If the overall comparison yields a significant F-statistic, pairwise comparisons can be performed without adjustment of the type 1 error because of the closure testing principle. This analysis will be performed using the FAS. In the case of significant F-statistic, we will report baseline adjusted means and their respective differences, including 95% confidence intervals.

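### SAP Section 2.3 ties 80% power to 29 patients per group in each disease, but its inputs give about 51% there; about 80% is reached by pooling UC and IBS, which the section does not say

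*SAP*

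**What the plan says.** SAP Section 2.3 powers the trial on GUT.EXPECT plus standard care against standard care alone. It sets out the inputs ("we assume a within-group standard deviation (SD) of 75 points" on the IBS-SSS) and says that "a difference of 40 points on the IBS-SSS can be detected with a power of 80" per cent at a two-sided 5% level "by including 29 patients per group, yielding a total sample size of n=87 for UC and IBS, respectively". It then allows 25% loss to the 3-month assessment and arrives at 117 randomised patients in each disease. Section 2.1 gives the total as 234, and Section 2.2 gives 1:1:1 allocation to three arms.

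Section 5.2.1 specifies one analysis of covariance over both diseases, adjusted for baseline IBS-SSS, with disease and sex as factors. It justifies pooling as follows: "Assuming no interaction effect between disease and treatment group, this is more effective than analysing both disease conditions independently". Pairwise comparisons follow only if the overall F-test is significant.

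Section 5.4.2 lists diagnosis as one of two key subgroups, under a heading of exploratory subgroup analyses. Subgroup-specific means and pairwise differences are reported when the interaction p-value is below 0.15.

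**The concern.** Since 87 is three times 29, the 29 is the number per arm within UC or within IBS. Section 2.3 attaches the 80% to that number and repeats the total for each disease. Nothing in the section says that the power refers to the two diseases combined, so its plain reading is 80% power in each disease. The section's own inputs do not give that.

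What is at stake is how results within a disease are read. Section 5.2.1 pools on the assumption of no disease-by-treatment interaction, and Section 5.4.2 makes diagnosis a key subgroup. If the interaction p-value falls below 0.15, separate estimates for UC and IBS will be reported. A reader who trusts Section 2.3 could then take a null result in one disease as coming from an adequately powered comparison, when the chance of detecting a 40-point difference was about one half.

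**Working it through.** **Inputs.** From Section 2.3: difference 40, SD 75 (standardised difference 40/75 = 0.533), two-sided alpha 5%, power 80%, 29 evaluable per group, 87 per disease, 25% loss, 117 randomised per disease. From Section 2.2: equal allocation to three arms. No baseline/follow-up correlation is given anywhere in the SAP.

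**1. Required size for the stated inputs.** Normal approximation:

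n per group = 2 × ((1.960 + 0.842) × 75/40)² = 2 × (5.254)² = 55.2, so 56.

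The exact t calculation gives 56.16, so 57. The plan's 29 is about half of this and is not reproduced for a comparison within one disease.

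**2. Power with 29 per group.** The standardised signal is 0.533 × √(29/2) = 2.031, and the normal approximation gives Φ(2.031 − 1.960) = 52.8%. The exact t calculation gives 51.4%. For 80% power with 29 per group, the standardised difference must be 0.7487, which is 0.7487 × 75 = 56.1 points.

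**3. Power after pooling UC and IBS.** 2 × 29 = 58 per arm. The signal is 0.533 × √(58/2) = 2.872, and the normal approximation gives Φ(2.872 − 1.960) = 81.9%. The exact t calculation gives 81.3%. This reproduces the stated 80%. The route is also visible in the figures: 57/2 = 28.5, rounded up to 29 per arm per disease.

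**4. Loss to follow-up.** 29/0.75 = 38.7, so 39 per arm per disease; 3 × 39 = 117 per disease; 2 × 117 = 234. This step is consistent with the plan.

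**5. Could another reading rescue 80% with 29 per group in one disease?**

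| Reading | Result |
|---|---|
| All 39 randomised per arm, no loss | 64–65% |
| One-sided 5% test at 29 per group (the plan says two-sided) | 64–65% |
| Baseline adjustment, correlation 0.3 | 55% |
| Baseline adjustment, correlation 0.5 | 63% |
| Baseline adjustment, correlation 0.6 | 70% |
| Baseline adjustment, correlation 0.7 | 80% |

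The adjustment rows use a residual SD of 75 × √(1 − ρ²). Reaching 80% needs a residual SD of 40/0.7487 = 53.4, so ρ = √(1 − (53.4/75)²) ≈ 0.70. The correlations are assumptions shown as a range. Section 2.3 presents 75 as the within-group SD and mentions no reduction for baseline.

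**The case against.** The strongest defence is that this is an omitted word, not a miscalculated trial. Every figure in Section 2.3 follows from a pooled calculation split over two diseases, the section speaks of powering the trial, and the primary analysis is pooled. This stands. A reader might infer from the 51% that the primary analysis is underpowered or that 234 patients are too few. The document does not support that: on the stated inputs, the pooled GUT.EXPECT versus standard care contrast has about 81% power before any gain from baseline adjustment.

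A second defence is that the SAP plans no confirmatory test within UC or within IBS. Diagnosis is a subgroup under an exploratory heading, without multiplicity adjustment. This also stands and limits the harm. It does not remove it, because diagnosis is singled out as key and the separate estimates may be reported.

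Third, one should not say that 80% holds only for the pooled contrast without qualification. The planned analysis adjusts for baseline, and a correlation near 0.70 would give 80% with 29 per group. The plan neither states nor relies on such a correlation.

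A reader might also go further and argue that the F-test gate in Section 5.2.1 brings even the pooled power below 80%. With 58 per arm and no baseline correlation, simulation puts the chance that both the F-test and the pairwise test are significant at about 77% if GUT.SUPPORT equals standard care and about 71% if it lies midway. These values rest on a GUT.SUPPORT mean and a zero correlation that the SAP does not give. At a correlation of 0.3 the range is about 76–82%, and at 0.5 about 84–89%. The gate does lower the pairwise power, but by an amount the document does not determine, so a shortfall below 80% is not established.

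**Conclusion.** The power statement in Section 2.3 is wrong as written. For an unadjusted comparison with SD 75, difference 40 and two-sided 5%, 80% power needs 57 per group, and 29 per group gives about 51%. The stated 80% is met by the pooled pairwise contrast with 58 per arm (about 81%), and the section omits to say so. The within-disease figure assumes 29 evaluable patients per arm and no credit for baseline adjustment; at correlations of 0.3 to 0.5 it would be 55–63%.

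The error lies in the description of the design. The sample size, the primary model and its tests are unaffected. It should be corrected before results are reported, but it does not put the primary analysis in doubt.

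**What to change.** Replace the power sentence in Section 2.3 with wording such as:

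> Twenty-nine evaluable patients per arm per disease, i.e. 58 per arm pooled over UC and IBS, give about 81% power for the pairwise contrast GUT.EXPECT+SC versus SC in the pooled primary analysis (difference 40, SD 75, two-sided 5%, no credit for baseline adjustment). Power within one disease is about 51% on the same inputs, so disease-specific comparisons are not powered.

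If the F-test gate of Section 5.2.1 is mentioned there, say that it lowers the pairwise power by an amount that depends on the GUT.SUPPORT mean and the baseline correlation, neither of which the plan gives. Do not enter a single gated power figure as a property of the design.

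The cost is a change of wording in the SAP. Enrolment and the primary analysis do not change.

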## 2.4 Framework

SOMA.GUT-RCT is planned to show that persistent gastrointestinal symptoms in UC and IBS can be improved by modifying dysfunctional symptom expectations and illness-related anxiety using expectation management strategies.

## 2.5 Statistical interim analyses and stopping guidance

No interim analyses will be conducted.

## 2.6 Timing of final analysis

The final analysis of the primary outcome will take place after the database has been reviewed for completeness and accuracy and database lock.

## 2.7 Timing of outcome assessments

The primary outcome was assessed at baseline and after 3 months follow-up. Secondary endpoints will be assessed at 6 weeks, 3 months, 6 months and 12 months after baseline.

# 3 Statistical Principles

## 3.1 Confidence intervals and *P* values

All applicable statistical tests will be two-sided and will be performed using a two-sided 5% significance level. Analyses of secondary outcomes will be performed exploratory, without adjustment for multiplicity. All confidence intervals presented will be 95% and two-sided.

## 3.2 Adherence and protocol deviations

At any point, patients in all three groups were able to quit the study.

## 3.3 Analysis populations

### 3.3.1 Full Analysis Set (FAS)

The primary analysis is based on the full analysis set (FAS). It is as complete as possible and as close as possible to the Intention-To-Treat (ITT) principle which includes all randomized patients, as belonging to their randomization arm, regardless of whether they refused therapy, or whether other protocol violations are known.

### 3.3.2 Intention to treat Population (ITT)

The primary analysis population is the ITT (intention to treat) population. The ITT population consists of all patients randomized.

### 3.3.3 Per Protocol population (PP)

The Per Protocol population includes all patients randomized who have no major protocol violation and for whom data is available from the follow-up measurement point.

Major protocol violations are any unapproved changes in the research study design and/or procedures that are within the investigator's control and not in accordance with

the IEC/IRB -approved protocol that may affect the participant’s rights, safety or well-being, or the completeness, accuracy and reliability of the study data.

Major protocol violation includes ineligible participants who were included in the trial by mistake, and those for whom the intervention or other procedure differed from that outlined in the protocol, or failure of consent process. Major protocol violations can occur at different times of the study and are defined in Table 1

Table 1: Major protocol violations at different times of study

Upon Inclusion:	
 
• IBS-SSS < 175 in the inclusion screening
 
• IBS-SSS < 75 in the baseline assessment (may differ from the inclusion screening)
 
• ROME IV criteria not fully met (IBS)
 
• No validated diagnosis of UC or IBS (doctor's letter or UKE/IK-confirmation)
 
• No guideline-appropriate treatment
 
• Missing or incomplete study consent
 
• Acute suicidality
 
• Acute illness requiring treatment (except UC/IBS)
 
• Psychotherapy in the last 3 months or currently starting psychotherapy
 
• Insufficient German language skills
 
• Significant cognitive deficits
 

At Baseline:	
 
• Unreported SAE
 

At 6-week follow-up:	
 
• 6-week follow-up completed before the 3rd intervention session (GUT.EXPECT, GUT.SUPPORT)
 

At 3-month follow-up:	
 
• More than 2 missing intervention sessions (GUT.EXPECT, GUT.SUPPORT)
 
• Data collection takes place before the booster session (GUT.EXPECT, GUT.SUPPORT)
 

At 12-month follow-up:	
 
• For IBS: missing telephone SKID interview, as the ROME IV criteria were not collected without it
 

### 3.3.4 Evaluated for Safety Set (EFS)

All randomized patients will be included into the Evaluated for Safety (EFS) set.

## 4 Trial Population

### 4.1 Eligibility

The absolute and relative (%) frequencies of ineligible participants recruited, if any, will be reported, with reasons for ineligibility.

### 4.2 Recruitment

The CONSORT diagram in Figure 4 of the design paper ([name], et al., 2022) will be updated with the actual recruitment figures.

### 4.3 Withdrawal/follow-up

The data of patients who have discontinued their participation in the study will be used if the patients have not objected to the use of their data. If patients discontinue treatment, efforts will be made to recruit them for further visits. We inquired causes for study withdrawal, reported them to the Data Safety & Monitoring Board (DSMB), and will report those in case of disclosure to clarify whether there are any differences between the intervention and control groups.

### 4.4 Baseline patient characteristics

Available baseline data consists of demographic data, medical history, and clinical information gathered in accordance with the goals of the overarching SOMACROSS research unit (see table 2 in ([name], et al., 2022)) and the project-specific data

- Symptom duration
- disease duration
- IBS-SSS
- SCCAI
- time between symptom onset and diagnosis
- time since the last treatment appointment due to bowel complaints
- time until the next treatment appointment due to bowel complaints
- time since last treatment appointment with the gastroenterologist
- number of inpatient treatments due to bowel complaints
- medication taken due to bowel complaints
- active disease (flare-up yes/no; UC only)

- duration of flare-up (UC only)
- time since last flare-up (UC only)
- fecal calprotectin
- CRP

will be summarized by descriptive statistics for the ITT population.

Categorical data will be summarised by numbers and percentages. Continuous data will be summarised by mean, standard deviation, median, interquartile range and range. Number of available observations and number of missing observations will be presented.

## 5 Analysis

### 5.1 Outcome definitions

#### 5.1.1 Primary outcome

The primary outcome for this study is the baseline to post-interventional change in gastrointestinal symptom severity (3 months follow-up). Gastrointestinal symptom severity will be assessed using the IBS-SSS questionnaire, which is applicable in both IBS and UC and validated in English and German in various forms of intestinal diseases. On a scale of 0–500, the IBS-SSS measures gastrointestinal pain, the degree of distension, satisfaction with bowel movement and the perceived impairment of quality of life during the past 10 days. For the German version of the IBS-SSS, a high sensitivity to assess changes in gastrointestinal symptom severity has been described.

#### 5.1.2 Secondary outcomes

Secondary outcomes include changes between baseline and follow-up measurements in total somatic symptom severity (PHQ-15), disease activity (Simple Clinical Colitis Activity Index, SCCAI), time since last treatment and utilisation of medical treatment, adverse effects and satisfaction with the intervention. C-reactive protein, and faecal calprotectin will be assessed at baseline and the 3 months post-intervention assessment. In addition, for patients whose blood was collected at the UKE, interleukin-6 and tumor necrosis factor (TNF- $\alpha$ ) will be assessed at both time points. Further secondary outcomes are illness-related anxiety (WI-7), psychological burden related to somatic symptoms or associated

health concerns (SSD-12), expectations of symptom severity, treatment outcome and coping with symptoms (TEX-Q; NRS).

The PHQ-15, SSCAI, WI-7, SSD-12 and TEX-Q are scored according to their questionnaire specific manuals.

Additionally, we will apply joint SOMACROSS core instruments. Supplements from the core set include adverse childhood experiences, neuroticism, negative affectivity, stigmatisation, healthcare use and diagnosis of somatic symptom disorder according to DSM-5. Most of these additional data will be collected at baseline and at the follow-up assessments, with the exception of the ACE-D, BFI-10, PANAS, TAS-20, ERQ and PSS10 questionnaires which are only collected at baseline.

## 5.2 Analysis methods

### 5.2.1 Primary outcome

An analysis of covariance will be used to investigate the group differences in the IBS-SSS, adjusted for baseline IBS-SSS. The underlying disease (UC vs IBS) and sex will be added as additional factors. Assuming no interaction effect between disease and treatment group, this is more effective than analysing both disease conditions independently. If the overall comparison yields a significant F-statistic, pairwise comparisons can be performed without adjustment of the type 1 error because of the closure testing principle. This analysis will be performed using the FAS. In the case of significant F-statistic, we will report baseline adjusted means and their respective differences, including 95% confidence intervals.

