#### 5.4.2 Subgroup analysis

Exploratory subgroup analyses aim at identifying subgroups which may especially benefit or do not respond well to the treatment groups offered, as measured by the reduction in gastrointestinal symptom severity (IBS-SSS). For this purpose, an ANCOVA for the IBS-SSS at 3 months as dependent variable will be performed in the ITT population, adjusted for the IBS-SSS at baseline and including group allocation as factor and the interaction between group and specified interaction variable. For each defined interaction variable, a separate ANCOVA model will be examined.

Interaction test p-values and. Subgroup-specific means and pairwise effect differences with 95% confidence intervals will be reported in the case of interaction tests with p values of less than 0.15 in accordance with the EMA guideline on the investigation of subgroups in confirmatory clinical trials. The presented p-values will not be adjusted for multiple comparisons.

The following subgroup variables will be investigated in separate ANCOVA models regarding their potential interaction with the intervention groups with respect to the change in the IBS-SSS from baseline to 3 months:

*Key subgroups*

- Diagnosis (UC vs. IBS)
- Gender (female vs. male; diverse patients are excluded for this analysis)

*Exploratory subgroups*

- Age (young [ $\leq$ first tercile] vs. middle aged vs. old [ $>$ third tercile])
- Migration background (none vs. 2nd generation [mother and/or father not born in Germany] vs. 1st generation [patient not born in Germany])
- Education ( $\leq$  10 years in school vs.  $>$  10 years in school)
- Duration of symptoms in years ( $<$ 5 years vs 5-10 years vs  $>$ 10 years)
- Baseline IBS-SSS none [0-74] vs mild [ $\geq$ 75-174] vs moderate [ $\geq$ 175 - 300] vs severe [ $>$ 300] ( this analysis will not be adjusted for baseline IBS-SSS)
- Somatic symptom severity (PHQ-15 categorical:  $<$ 10 vs  $\geq$ 10)
- Somatosensory Amplification (SSAS split at median ( $\leq$ 15 vs  $>$  15))
- PHQ-15 categorical:  $<$ 10 vs  $\geq$ 10)
- GAD-7 categorical:  $<$ 10 vs  $\geq$ 10
- TAS-20 as 20-60 vs  $\geq$  61
- ERQ suppression split at median ( $\leq$ 3.25 vs  $>$  3.25)
- SSD-12  $<$  24 vs  $\geq$  24
- Adverse childhood events (ACE-D: 0 vs. 1-3 vs.  $\geq$  4)
- BMI ( $<$  18,5 vs.  $\geq$  18,5 to 24,9 vs.  $\geq$  25)

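### The primary test answers for UC and IBS on average, but the stated aim and the sample-size text read as if it answered for each disease

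*SAP*

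**What the plan says.** **Aim.** Section 2.4 says the trial is "planned to show that persistent gastrointestinal symptoms in UC and IBS can be improved" by expectation management. It does not say whether this means in each disease or on average over both. Section 1.2 gives as a reason for studying the two diseases in parallel that one can see whether the same mechanisms sustain symptoms in both.

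**Sample size.** Section 2.3 powers the comparison of GUT.EXPECT plus standard care with standard care alone. It says "we assume a within-group standard deviation (SD) of 75 points" and takes a difference of 40 points, 80% power and a two-sided 5% level. These are met, it says, "by including 29 patients per group, yielding a total sample size of n=87 for UC and IBS, respectively". With 25% loss to follow-up this becomes 117 randomised per disease.

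**Primary analysis.** Section 5.2.1 fits one ANCOVA over both diseases, adjusted for baseline IBS-SSS, with disease and sex as additional factors and no group-by-disease term. The reason given is: "Assuming no interaction effect between disease and treatment group, this is more effective than analysing both disease conditions independently". A significant overall F test opens unadjusted pairwise comparisons.

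**Differences between diseases.** Section 5.4.2 lists diagnosis first among its key subgroups and tests the group-by-diagnosis interaction, in a section introduced as exploratory. Subgroup means and pairwise differences with confidence intervals follow only when the interaction p-value is below 0.15. No rule links that result to the primary conclusion.

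**The concern.** The pooled contrast estimates an average over UC and IBS. With equal numbers per disease, an effect confined to one disease appears as half its size in the pooled contrast and can still be significant. The wording of 2.4 would then let a reader conclude that both diseases improve.

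The SAP's safeguard is the interaction test, but 5.4.2 makes the disease-specific differences depend on it, and the trial is too small for that test to be a reliable screen. When it stays silent, no estimate for UC or for IBS is called for. Yet 1.2 makes similarity across the two diseases a question of the trial, while 5.2.1 assumes it.

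The sample-size text adds to this. Someone who takes 2.3 to mean 80% power with 29 per group inside each disease would think each disease had been adequately tested.

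**Working it through.** **Inputs.** From SAP 2.3: SD 75, difference 40, two-sided 5%, power 80%, 29 evaluable per group and disease, 25% loss. From 5.2.1: overall F test, then pairwise test. From 5.4.2: interaction screen at p<0.15. Assumptions made here: 75 is the residual SD (no gain from baseline adjustment), the two diseases are equal in size, and the GUT.SUPPORT effect lies between 0 and half of the GUT.EXPECT effect.

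**1. The plan's own number.**
- Normal approximation: n per arm = 2 × (1.960 + 0.842)² × 75² / 40² = 2 × 7.85 × 3.516 ≈ 55.2, so 56. The t-test gives 56.2, so 57.
- 57 / 2 = 28.5, so 29 per arm in each disease, or 58 per arm over both. The stated 29 is therefore the pooled requirement split across two diseases.
- Loss: 29 / 0.75 = 38.7, so 39 per arm, and 3 × 39 = 117 per disease. This reproduces.

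**2. Power for 40 points.** The standard error is 75 × √(2/n).

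| Comparison | n per arm | SE | 40/SE | Power (normal) | Power (t) |
|---|---|---|---|---|---|
| Within one disease | 29 | 19.7 | 2.03 | 53% | 51% |
| Pooled | 58 | 13.9 | 2.87 | 82% | 81% |

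For 29 against 29 to have 80% power, the residual SD would have to be about 54, or the baseline-outcome correlation about 0.69. Section 2.3 states neither. If the overall F test must also be significant, as 5.2.1 requires, simulated power of the pooled rule is about 71-77%.

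**3. Effect in one disease only (40 and 0 points).** The pooled difference is (40 + 0)/2 = 20 points. 20/13.9 = 1.44, so the pairwise test alone rejects in about 30% of trials. Simulating 2 diseases × 3 arms × 29 patients, with at least 20,000 trials per scenario, gives:

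| Event | Share of trials |
|---|---|
| F test and GUT.EXPECT versus SC both significant, GUT.EXPECT favoured | 20-21% |
| Interaction p<0.15 (2 degrees of freedom) | 42-50% |
| Pooled win and interaction p≥0.15 | about 11% |

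So about half of the pooled wins in this scenario (11 of 20-21) carry no interaction flag, and 5.4.2 would then not call for a result in either disease.

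**4. Level check.** With no effect in either disease, the overall F test rejects in 4.8-5.0% of trials. The stated 5% holds for the hypothesis that is tested.

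**The case against.** Pooling is a legitimate and common choice, and 5.2.1 states its assumption openly. The document names one deciding analysis and sets separate analyses aside. Diagnosis is a key subgroup with a lenient threshold. The scenario of full effect in one disease and none in the other is one extreme. All of this stands, and none of it requires a change to the primary test.

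Three stronger readings are tempting, and the document does not support them.

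- *The type I error is inflated several-fold.* It is not. If one disease responds, the pooled null hypothesis is false, and rejecting it is correct. The 20-21% would be an error rate only if success were defined as an effect in each disease, and the SAP does not define it so.
- *The trial was sized for a separate comparison in each disease.* The wording of 2.3 suggests this, but the arithmetic shows the pooled size split in two. Sample size and primary analysis agree; the text of 2.3 is what misleads.
- *A claim for a disease should require significance in that disease.* With about 50% power per disease, such a rule would often deny a true effect. With 40 points in both diseases, separate tests succeed in both in only about 26% of trials. That trade-off is debatable and is not proposed here.

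What the objection does not answer is that the aim can be read in two ways, that 2.3 can be read as 80% power per disease, and that estimates by disease depend on a weak screen.

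**Conclusion.** The concern holds as a mismatch between what is tested and what the text lets a reader conclude. It is not a fault in the level or the size of the pooled test. At the planned effect confined to one disease, a pooled win occurs in about one trial in five, and about half of those wins come without an interaction flag. Power within one disease is about 51-53%, not 80%.

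The figures rest on SD 75 as the residual SD, equal disease sizes and 29 evaluable per arm and disease. They move with the inputs: if all 39 per arm and disease were evaluable, the pooled rule would succeed in 27-29% of trials in the same scenario. A gain from baseline adjustment would also raise that rate, and would raise power within each disease.

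**What to change.** - **Sections 2.4 and 5.2.1:** state that the primary conclusion concerns the average effect of GUT.EXPECT versus SC over the pooled UC and IBS population.
- **Section 2.3:** state that the 80% power belongs to the pooled contrast at 58 evaluable patients per arm, and that power within one disease is about 50% on the same inputs. Add that requiring the F test as well lowers the pooled power to about 71-77%.
- **Sections 5.2.1 and 5.4.2:** whatever the interaction p-value, report the GUT.EXPECT versus SC difference in UC and in IBS with 95% confidence intervals, together with the interaction estimate. Take them from the primary ANCOVA with a group-by-disease term added.

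The cost is one extra model and some wording, with no extra patients and no change to the pooled primary test. The drawback is a less favourable stated power per disease and wide intervals: about ±39 points within one disease (1.96 × 19.7), against ±27 pooled (1.96 × 13.9). Those widths show the reader how much the trial can say about each disease.
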